10.3 Treatment Assignment Procedures

10.3.1 Randomization Procedures

Within each biopsy cohort (Rectal Mucosal Biopsy Cohort and No Rectal Mucosal Biopsy Cohort), subjects will be randomized 4:1 to 4CMenB or placebo. Randomization will be stratified by sex. Approximately twenty (20) subjects, approximately 10 males and 10 females, will be enrolled into the Rectal Mucosal Biopsy Cohort and approximately 30 subjects, approximately 15 males and 15 females, will be enrolled into the No Rectal Mucosal Biopsy Cohort.

The list of randomized treatment assignments will be included in the enrollment module of Emmes' Internet Data Entry System (IDES). Advantage eClinical® will assign each enrolled participant to a treatment arm after demographic and eligibility data have been entered into the system. A designated individual at each participating site will be provided with a coded list for emergency unblinding purposes, which will be kept in a secure place.

Instructions for use of the enrollment module are included in the Advantage eClinical User's Guide. Manual back-up procedures and instructions are provided for use in the event that a participating site temporarily loses access to the Internet or the online enrollment system is unavailable.

10.3.2 Masking Procedures

This is a double-blinded clinical trial. Participants, site investigators, and study personnel who perform study assessments following study product administration, data entry personnel at the sites, and laboratory personnel performing study assays will be blinded to treatment assignment. Syringes will be labeled with an overlay/blinding tape containing the subject ID, and the treatment number from the treatment key, and expiration time for the syringe, and provided to the unblinded vaccine administrator. The unblinded vaccine administrator will be credentialed to administer vaccines but will not be involved in study-related assessments, subject contact, or data collection following vaccination (data entry related to the vaccination is acceptable).

The randomization scheme will be generated by the Statistical and Data Coordinating Center (SDCC) and provided to unblinded study personnel (i.e., research pharmacists performing study product preparations and unblinded study product administrators) at the participating sites. The unblinded study product administrator is a study personnel member credentialed to administer study product and may also participate in dose preparation but will not be involved in study-related assessments or have participant contact for data collection following study product administration to the participant.

The SMC may receive data in aggregate and presented by study arm. The SMC may be unblinded to individual study treatment assignments, as needed, to adequately assess safety issues. The SMC will review grouped and unblinded data in the closed session only.

10.4 Planned Interim Analyses

10.4.1 Interim Safety Review

As defined in the charter, the SMC will review data at specified times during the course of the study for subject and overall study progress, and will conduct ad hoc reviews as appropriate when a halting rule is met or for immediate concerns regarding observations during this study.

10.4.2 Interim Immunogenicity Review

There will be an interim immunogenicity analysis, which may be used to optimize and prioritize research laboratory assays for exploratory outcomes. Results of the interim analyses will not be used to make any decisions concerning the conduct of this trial.

The interim immunogenicity analysis will include all available antibody data for the first 20 subjects who complete Visit 6, which includes data addressing the primary and secondary objectives, as well as several exploratory objectives. The interim report will be prepared by the unblinded statistician at the SDCC after all relevant immunogenicity data through Visit 6 are received. Results will be shared only with relevant study personnel (i.e. PI, laboratory investigator(s), and DMID) and only in aggregate by treatment arm. Study personnel will remain blinded to individual subject treatment assignments.

The interim immunogenicity analyses will include summaries of descriptive and aggregate antibody data against antigens from *Neisseria gonorrhoeae* and *Neisseria meningitidis* stratified by antigen, specimen type (serum and mucosal sites), pre- versus post-treatment timepoints, and treatment arm (4CMenB or placebo). No hypothesis tests or modeling will be included in the interim immunogenicity analysis. This interim analysis of the data is not intended to impact the conduct of this trial. No statistical adjustments are planned.

10.5 Final Analysis Plan

A separate Statistical Analysis Plan (SAP) will be written that will contain the details of all planned analyses. This section outlines the major components of the analyses.

10.5.1 Analysis Populations

10.5.1.1 Immunogenicity Population

For the primary outcome analysis, the Immunogenicity Population at a specified follow-up visit will include all eligible subjects who have received all doses of study product prior to that visit and have immunogenicity data available for that visit. Subjects will be classified according to the study product received. To account for subjects having data available only for a subset of assays, assay-specific populations will be defined.

Per-protocol populations may also be defined that further restrict the immunogenicity analysis populations to exclude subjects with major protocol deviations or events that may impact study product effectiveness or the ascertainment or interpretation of assay results. These will be described in the SAP. For supplementary and exploratory analyses, additional analysis populations may be defined; details will be provided in the SAP.

10.5.1.2 Safety Population

The Safety Population will include all subjects who received at least one dose of study product. Subjects will be classified according to the treatment received.

10.5.2 Baseline Characteristics

Baseline and demographic characteristics will be summarized overall and by study arm. For both continuous and categorical variables, appropriate summary statistics will be applied. For continuous variables, descriptive statistics will include the number of non-missing values, mean, standard deviation, median, minimum, and maximum. For categorical variables, descriptive statistics will include counts and percentages per category.

10.5.3 Immunogenicity Analysis Plan

For the analyses of the primary and secondary immunogenicity outcomes, the GMT and geometric mean fold rise (GMFR) for ELISA titers will be calculated for Days 1, 29, 43, 57, and 181 in each study arm. Point estimates and their 95% confidence intervals will be reported for each time point. The distribution of titers will also be graphically summarized using reverse cumulative frequency distributions. Anatomical sites will be summarized separately.

Summaries of the ratio of serum to mucosal IgG concentration will be generated at each time point. Geometric means and confidence intervals will be reported and scatter plots of serum vs. mucosal IgG concentrations will be generated. Summaries of pairwise concentration ratios, comparing anatomical sites, will also be generated at each time point. Summaries will include geometric means and confidence intervals as well as graphical summaries.

All geometric mean calculations will use \log_{10} transformed data, and the anti-log of the resulting point estimates will be reported for means and confidence intervals. Missing immunogenicity data will not be imputed and no search for outliers will be performed. The logarithmic transformation is used to improve the distributional properties of the immunogenicity data to reduce the impact of potential outliers.

Additional supplementary and/or sensitivity analyses of the primary and secondary outcomes as well as analysis of the exploratory immunogenicity outcomes will be described in the separate SAP.

10.5.4 Safety Analysis Plan

Safety evaluations will be based on the frequency and severity of reactogenicity events, AEs, and SAEs occurring from the time of first study product administration through the final study visit.

AEs and SAEs will be coded by Medical Dictionary for Regulatory Activities (MedDRA®) for preferred term and system organ class. The rate and exact 95% CIs of AEs and SAEs in aggregate, as well as by MedDRA categories, will be computed. The number of SAEs will be reported by a detailed listing showing the type, MedDRA coding, relevant dates (treatment dosing date(s) and SAE onset and resolution dates), severity, relatedness, and outcome for each event.

Solicited local injection site and systemic reactogenicity will be summarized by severity for each day post injection (for each injection) and as the maximum severity over the entire assessment period (across injections). Additionally, solicited AEs will be analyzed by taking the most severe response over the follow-up period, dichotomizing into a binary variable (none vs. any severity) and using exact confidence intervals to summarize the proportion/percentage of subjects reporting each symptom any infection site symptom, and any systemic symptom. Solicited AEs will be summarized separately for each infection, and over both injections by study arm.

Vital sign and physical exam findings will also be summarized and/or provided in subject-level listings.

Missing safety data will not be imputed and no search for outliers will be performed.

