3 STUDY DESIGN, OBJECTIVES AND ENDPOINTS OR OUTCOME MEASURES

3.1 Study Design Description

This is a single-center phase 2 double blinded mechanistic clinical trial to assess the systemic and mucosal immunogenicity of the multicomponent meningococcal serogroup B vaccine (4CMenB or Bexsero®) against GC, using a placebo vaccine (normal saline) as a comparator.

This trial will enroll approximately 50 healthy male and non-pregnant female subjects aged 18 to 49 years, inclusive, who meet all eligibility criteria. Subjects will be randomized 4:1 to one of two treatment groups. Group 1 (approximate N=40) will receive two doses of 4CMenB on Day 1 and Day 29. Group 2 (approximate N=10) will receive two placebo injections on Day 1 and Day 29. *The goal will be to ensure adequate representation of subjects by sex in both groups (Table 1)*

Vaccine preparation and administration will be unblinded. Only pharmacy personnel, the Emmes unblinded team and an unblinded vaccinator will have access to the study codes, and all other study personnel will be blinded. Subjects will be followed through 6 months after their first vaccination (Day 181).

All subjects will undergo sampling of mucosal secretions for testing for antibodies against GC. Male subjects will undergo oropharyngeal and rectal mucosal sampling, and female subjects will undergo oropharyngeal, vaginal and rectal mucosal sampling. A subset of subjects in each treatment group (N=16 in Group 1, N=4 in Group 2) will undergo rectal mucosal biopsy at two time points (baseline and following the second vaccination) for assessment of tissue GC specific cellular responses. *The goal will be to ensure adequate representation of subjects by sex in both groups in the rectal mucosal biopsy cohort (Table 1).*

This trial is expected to take approximately 14 months to complete, from initiation through availability of a final report on the primary outcomes of mucosal antibody responses and the secondary outcomes of serum antibody responses and safety outcomes related to mucosal sampling procedures and 4CMenB vaccination. For additional details on study procedures and evaluations and study schedule by study visits/days, see [Sections 6, 7, and 8](#) and well as Appendices [Appendix A](#) and [Appendix B](#).

Schematic of Study Design: See [Table 1](#).

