8.1.1 Adverse Events

ICH E6 defines an AE as any untoward medical occurrence in a patient or clinical investigation subject administered a pharmaceutical product regardless of its causal relationship to the study treatment. FDA defines an AE as any untoward medical occurrence associated with the use of a drug in humans, whether or not considered drug related.

An AE can therefore be any unfavorable and unintended sign (including an abnormal laboratory finding), symptom, or disease temporally associated with the use of medicinal (investigational) product. In addition, AEs specific to the rectal mucosal biopsy cohort will be collected prior to study drug administration and are defined as any unfavorable and unintended sign, symptom, or disease temporally associated with the rectal mucosal biopsy procedure. The occurrence of an AE may come to the attention of study personnel during study visits and interviews of a study recipient presenting for medical care, or upon review by a study monitor.

All AEs, including solicited local (injection site) and systemic (subjective and quantitative) reactions, will be captured on the appropriate eCRF. Information to be collected for AEs includes event description, date of onset, assessment of severity, relationship to study product and alternate etiology (assessed only by those with the training and authority to make a diagnosis and listed on the Form FDA 1572 as an investigator), date of resolution, seriousness and outcome. AEs occurring during the trial collection and reporting period will be documented appropriately regardless of relationship. AEs will be followed through resolution.

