8.3 Reporting Procedures

Any medical condition that is present at the time that the subject is screened will be considered as baseline and not reported as an AE. However, if the severity or frequency of any pre-existing medical condition worsens, it should be recorded as an AE.

If an event meets both the criteria of a study endpoint and an AE, the event will be reported either as a study endpoint or as an AE (not both).

For the rectal biopsy cohort, SAEs will be documented and reported from the time of the baseline rectal mucosal biopsy through approximately 6 months after the first study vaccination. For the non-rectal biopsy cohort, SAEs will be documented and reported from the first study vaccination through approximately 6 months after the first study vaccination.

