9.3. Adverse Events

Unsolicited AEs and SAEs will be coded by MedDRA for preferred term (PT) and system organ class (SOC). AEs will also be graded for severity. For each AE experienced, the participant will be asked if he/she had received medical attention, defined as hospitalization, an ER visit, or an otherwise unscheduled visit to or from medical personnel for any reason. AEs characterized by such unscheduled medical care will be designated as MAAEs. Safety will be assessed by the frequency and severity of:

- Any AE related to 4CMenB immunization through the end of the study.
- Any AE related to rectal mucosal sampling procedures through the end of the study.
- Any SAEs through the end of the study

A summary of all adverse events is provided in **Table 51**. This information is also presented graphically in **Figure 88** with number and severity of AEs categorized by MedDRA System Organ Class and treatment group. A summary of those events that occurred in $\geq 5\%$ of participants in any treatment group is provided in **Table 54**.

9.3.1. **Solicited Events and Symptoms**

Systemic solicited adverse events were collected pre-vaccination, and systemic and local solicited adverse events were collected 30 minutes post-vaccination and then daily for 7 days after each vaccination and graded on a severity scale of 0 (absent), 1 (mild), 2 (moderate) and 3 (severe). Systemic events include fever, chills/shivering/sweating, fatigue, malaise, myalgia and arthralgia (exclusive of the injection site), headache, and nausea. Local events include pain at injection site, pruritus, erythema, ecchymosis, induration/swelling, pain, and tenderness. **Table 56** summarizes the solicited adverse event grading scale.

The proportion of participants reporting at least one solicited adverse event will be summarized for each solicited adverse event, any systemic symptom, any local symptom, and any symptoms. The 95% CI will be calculated using Clopper-Pearson methodology from a binomial distribution (**Table 55**).

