For each systemic and local event, any systemic event, any local event, and any solicited event, the maximum severity over 7 days after each vaccination will be summarized for the safety population. The number and percentage of participants reporting each event will be summarized by the maximum severity and treatment group, separately for each vaccination and over all vaccinations. For each event the denominator is the number of participants with non-missing data for the specific event (**Table 55**).

The number of participants reporting a solicited adverse event will be summarized for each day post vaccination for each vaccination and for all vaccinations combined both in a summary table (**Table 56**, **Table 7**, **Table 58**, and **Table 59**) and graphically in a bar chart (**Figure 89** and **Figure 90**). A comparison of the event rate for each treatment group between dose 1 and dose 2 will be presented in **Table 60**.

Solicited adverse events by participant will be presented in **Listing 23** and **Listing 24**.

9.3.2. **Unsolicited Adverse Events**

When calculating the incidence of unsolicited AEs (i.e., on a per participant basis), each participant will only be counted once at the highest severity and/or relationship, and any repetitions of AEs within a participant will be ignored; the denominator will be the total number of participants in the safety population. All AEs reported will be included in the summaries and analyses.

The number and percentage of participants reporting at least one unsolicited AE will be summarized by MedDRA system organ class and preferred term. Denominators for percentages are the number of participants who received the study vaccination summarized. A 95% CI will be presented for the percentage of participants reporting any unsolicited AE (serious or non-serious) for each MedDRA system organ class and preferred term. A listing of all unsolicited AEs by participant will be presented in **Listing 25**, sorted by Treatment group, participant ID, and AE Number.

The following summaries for unsolicited adverse events will be presented by MedDRA system organ class, preferred term, and Treatment group:

- Participant incidence and total frequency of unsolicited adverse events with 95% CI (**Table 61**)
- Summary of severity and relationship to study product (**Table 62**)

- Participant incidence and total frequency of related unsolicited adverse events over time (Days 1-7) ([Table 63](#))

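### Protocol 10.5.4 starts safety counting after the baseline biopsy, in conflict with Protocol 8.1.1 and 8.3 and with the SAP; SAP Table 51 mislabels its biopsy row and sets it against the whole arm

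*Protocol*

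**What the plan says.** **Start of counting.** Protocol 10.5.4 counts events "occurring from the time of first study product administration through the final study visit". Protocol 8.1.1 states that "AEs specific to the rectal mucosal biopsy cohort will be collected prior to study drug administration", and Protocol 8.3 that, for the biopsy cohort, "SAEs will be documented and reported from the time of the baseline rectal mucosal biopsy". Protocol 8.1 and 8.2 name AEs of rectal mucosal sampling as a safety parameter. SAP 9.3 repeats it ("Any AE related to rectal mucosal sampling procedures through the end of the study"), and SAP 9.3.2 adds: "All AEs reported will be included in the summaries and analyses". Protocol 10.5 defers to the SAP for detail: "A separate Statistical Analysis Plan (SAP) will be written that will contain the details of all planned analyses".

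**Who is biopsied, and when.** Protocol 3.1 gives "N=16 in Group 1, N=4 in Group 2) will undergo rectal mucosal biopsy at two time points". The first biopsy is Visit 00C, Day -28 to -14. Randomization and first dose follow at Visit 01 (Protocol 6.2.1). The second biopsy is at Day 43.

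**Population.** Protocol 10.5.1.2 and SAP 6.3.3 both require at least one dose for the Safety Population, and SAP 9 presents all safety summaries on it.

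**Table 51.** Its single biopsy row is worded as a solicited event, and its note sets N to the Safety Population. Protocol 8.2.1 ties solicited events to study product; 8.2.2 places events after rectal biopsy among the unsolicited ones.

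**The concern.** The biopsy is an invasive procedure done only for research, and its safety is something both documents say they will assess. Three features of the plan work against that.

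- Read alone, the Protocol's analysis section drops events that its own safety section collects.
- The one summary row for biopsy events has a label that contradicts the Protocol's definitions, and a column N in which most people were never biopsied.
- A volunteer who is biopsied and then not dosed falls outside the only safety population. A biopsy complication could itself be the reason for not dosing, so this exclusion may depend on the outcome.

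With so few events likely, one omission or one wrong denominator would decide the reported rate.

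**Working it through.** **1. Cohort sizes.** Protocol Table 1: biopsied 8+8 = 16 (4CMenB) and 2+2 = 4 (placebo), 20 in all. Not biopsied: 12+12+3+3 = 30. Arms: 40 and 10, total 50. These agree with Protocol 3.1.

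**2. Window.** Two biopsies each: 20 × 2 = 40 planned, of which 20 precede first dose. 20/40 = 50% lie outside the 10.5.4 window.

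**3. Where a baseline-biopsy AE can appear under the SAP.**

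| Output | Dosed participant | Biopsied, never dosed |
|---|---|---|
| Tables 51, 54, 62 | Possible | No (Safety Population only) |
| Listing 25 | Possible | No treatment group or dose to list under |
| Table 61 (the 95% CIs of SAP 9.3.2) | No: columns are post dose 1, post dose 2 and post any dose | No |

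The SAP is also uneven on scope: 4.5.2 omits the sampling-procedure parameter that 9.3 includes. For the Day 43 biopsy the window is not an issue; only label and denominator are.

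**4. Denominator.** Ratio of biopsied to whole: 16/40 = 4/10 = 20/50 = 0.4, a 2.5-fold difference. One participant with a biopsy AE, with Clopper-Pearson limits (the SAP's exact method):

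| | Biopsied as denominator | Table 51 N as denominator |
|---|---|---|
| 4CMenB | 1/16 = 6.25% (0.2 to 30.2) | 1/40 = 2.5% (0.1 to 13.2) |
| Placebo | 1/4 = 25% (0.6 to 80.6) | 1/10 = 10% (0.3 to 44.5) |
| All | 1/20 = 5% (0.1 to 24.9) | 1/50 = 2% (0.1 to 10.6) |

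The right-hand column applies if Table 51's stated N is the denominator, or if the event is classed as unsolicited, because SAP 9.3.2 then divides by the whole Safety Population.

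**5. Expected events, as a guide.** Protocol 2.3.1 cites 16 related AEs in 1,004 procedures: 16/1004 = 1.59%, which reproduces its 1.6%. For 20 baseline biopsies: 20 × 0.016 = 0.32 expected, and the chance of at least one is 1 − 0.984^20 = 27.6%. The cited series used flexible sigmoidoscopes (its title says so in the reference list). This trial uses rigid ones, for which Protocol 2.3.1 presumes fewer complications, so these figures are probably high.

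**6. Biopsied but never dosed.** The documents give no number. If u people are biopsied and not dosed, on top of 20 who are, the share of baseline biopsies in no rate is u/(20+u). For an assumed u of 0, 1, 2, 3 or 4 this is 0, 4.8, 9.1, 13.0 or 16.7%. The range is illustrative only.

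**The case against.** The best answer is that Protocol 10.5 offers only an outline and hands the detail to the SAP. The SAP has no first-dose start, names procedure AEs as a safety parameter and includes every reported AE. A reader might infer from 10.5.4 that half the biopsies will be missing from the final report. The documents do not support that: the loss holds on the 10.5.4 wording, not on the SAP's. What remains is a contradiction that nobody has resolved, plus a confidence-interval table with no place for a pre-dose event. Keeping pre-randomization events out of a by-dose, by-arm table is defensible, but the plan then needs to say where they go.

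On Table 51, the rule of dividing by non-missing data (SAP 9 and 9.3.1) could yield 16 and 4 if the row really were solicited, so the 2.5-fold understatement is not certain. It does follow from the table's own N, and from the unsolicited rule once the label is corrected. A reader could also recompute the rate, since Table 6 gives biopsy-cohort sizes by arm. That is a workaround for an unclear table and does not clear it up.

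Two further stronger readings should be resisted. Protocol 3.1 speaks of secondary outcomes that include "safety outcomes related to mucosal sampling procedures and 4CMenB vaccination", which might suggest that a secondary endpoint goes unanalysed. The formal lists (Protocol 3.3.2, SAP 3.2.2) name only AEs related to 4CMenB and SAEs, so procedure AEs are a safety parameter and not a listed endpoint. Nor are undosed volunteers left unprotected: SAE reporting from the baseline biopsy (Protocol 8.3) and the procedure-related halting rule (8.6.1) both cover them. Only their place in a tabulated rate is missing.

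**Conclusion.** Wrong as written, and minor. Protocol 10.5.4 conflicts with Protocol 8.1.1, 8.2 and 8.3 and with SAP 9.3 and 9.3.2 on when counting starts. Table 51's biopsy row carries the wrong class of event and, on its stated N, the wrong set at risk, which would shrink each biopsy percentage to 0.4 of its value among those biopsied. Both Safety Populations exclude anyone biopsied but never dosed.

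The sizes assume the planned 16 and 4 biopsied, all of them dosed, with arms of 40 and 10. How many people are biopsied and never dosed cannot be derived from the documents. The primary endpoint and the listed secondary endpoints are untouched, and fewer than one baseline-biopsy AE is expected at the cited rate.

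**What to change.** (a) In Protocol 10.5.4, count biopsy-related AEs and all SAEs from the baseline biopsy for the biopsy cohort, matching 8.1.1 and 8.3. Do not simply move the start date for all AEs: Appendix A limits the Visit 00C review to biopsy AEs, so a general shift would bring in other pre-dose events for one cohort only. State in SAP 9.3.2 that these events are included and flagged as before first dose.

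(b) Relabel the Table 51 row as unsolicited AE related to rectal biopsy, with biopsied, dosed participants as its denominator (planned 16 and 4), and record this as an exception to the 9.3.2 rule. AEs of rectal secretion sampling keep the whole Safety Population, since everyone has that procedure (Protocol 7.1.1).

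(c) Add one small table of biopsy-related AEs with exact 95% CIs for everyone biopsied, dosed or not. Pool baseline-biopsy events over arms, because they precede randomization, and show Day 43 events by arm. Footnote Table 61 to it.

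The cost is one small table, one relabelled row, some SAP wording and a short Protocol change that needs IRB approval (Protocol 9.1). The events are already reviewed at Visits 00C, 00P, 06 and 06P. Protocol 8.1.3 asks for relationship to procedure for SAEs, whereas 8.1.1 mentions only relationship to study product. The case report form is not in the documents, so check that it records relationship to procedure for non-serious AEs.
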